Our long-term goal is to determine the pathophysiology of SD and related disorders, such as VT, and develop new diagnostic and treatment options for these patients. The objective of this application is to identify brain abnormalities in SD and SD/VT patients as the basis for characterization of central mechanisms underlying symptom improvement following the use of sodium oxybate. Our central hypothesis is that, compared to SD patients, SD/VT patients will have additional brain abnormalities within the sensorimotor brain circuits controlling voice production, which are being modulated to a greater extent with sodium oxybate treatment. We further postulate that the clinical efficacy of sodium oxybate treatment will correlate with its central modulatory effects. The rationale for the proposed research is that identification of distinct brain mechanisms underlying SD and SD/VT clinical manifestations would provide the necessary insights into the pathophysiology of these disorders, while understanding the neural correlates of sodium oxybate action would allow establishment of a scientific rationale for the use of a novel treatment in these disorders.

We propose the following two specific aims:

1. Determine disorder-specific brain abnormalities in SD and SD/VT patients. Based on our preliminary data, our *working hypothesis* is that distinct brain abnormalities will be present in SD and SD/VT patients, who also share common abnormalities within the sensorimotor brain networks controlling voice production.

2. Characterize the central effects of sodium oxybate treatment in ethanol-responsive SD and SD/VT patients. Based on our preliminary data, our *working hypothesis* is that the greater beneficial effects of sodium oxybate treatment in SD/VT patients compared to SD patients are due to a greater extent of modulation of their abnormal brain activation.

At the completion of these studies, it is our expectation that we will have (i) identified characteristic profiles of brain abnormalities in SD and SD/VT patients, (ii) determined the extent of their modulation with a novel treatment, sodium oxybate, both of which will be critical for (iii) establishment of neural markers and a new therapeutic option for patients who do not benefit from botulinum toxin treatment alone. These results are expected to have an important positive impact, because they will fundamentally advance our knowledge of the pathophysiology of SD and VT as well as allow for improved treatment.

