For group analysis, the 3-D anatomical datasets of each subject will be spatially normalized and converted to the standard anatomical space. The resulting normalization parameters will be applied to the 4-D time series datasets. To estimate the main effect of a task per group, the group analysis will be carried out using a three-way analysis of variance (ANOVA) with subject as a random factor and the task and group as fixed factors ($p \leq 0.025$, voxelwise corrected) to identify (1) shared abnormalities in all patients vs. controls, and (2) distinct abnormalities between SD vs. SD/VT patients. Statistical differences in brain activation extent will be assessed using the subtraction method within the three-way ANOVA design. This univariate data analysis will provide information about the extent and intensity of brain activation in different groups (i.e., SD and SD/VT patients vs. controls and SD patients vs. SD/VT patients).

To further our knowledge of functional brain abnormalities in SD and VT, we will perform multi-stage brain network analysis, which will allow for identification of abnormal brain networks and the relationship between the key network regions, possibly contributing to the pathophysiology of these disorders. For this, we will first perform a correlation analysis between functional and structural datasets in SD and SD/VT patients to determine the brain regions of abnormal function with underlying structural changes. The structural data will be derived from the *Studies 1.3.2 and 1.3.3*.

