The proposed studies, from univariate analysis to network modeling, are expected to provide full characterization of shared and distinct functional brain abnormalities between SD and SD/VT patients. This approach is feasible in our hand because we have already used similar analysis techniques in our previous studies ([name] et al., 2009; [name] and Ludlow, 2010, 2011).

Study population and Sample size. To estimate the number of subjects to be included in this study, we reviewed our recent fMRI study in SD patients, which used the similar fMRI experimental design ([name] and Ludlow, 2010). Significantly increased activation intensity was found in the primary somatosensory cortex during production of symptomatic syllables in SD patients compared to controls (mean % signal change \pm s.d.: SD vs. controls: 0.63 ± 0.16 vs. 0.39 ± 0.23 ; $p \leq 0.01$). Using these values, results of two-tailed t -test calculations suggest that a sample size of 15 subjects per group would have 80% power to detect group differences at a 0.025 significance level. The power for network analyses is the same. We propose to recruit 20 subjects per group to account for the subjects' dropout possibilities and to increase statistical power for detection of differences between groups.

1.3.2 Study #2: Mapping disorder-specific gray matter abnormalities in patients with SD vs. SD/VT using high-resolution MRI. In this study, we propose to identify GMV abnormalities that are common and distinct between SD and SD/VT patients. VBM is the most commonly used technique to identify changes in both cortical and subcortical gray matter in response to physiological and pathological conditions. To obtain VBM measures, we will acquire whole-brain high-resolution MR images (voxel size ≤ 1 mm isotropic) on a 3.0 Tesla Philips scanner within the same session of fMRI study described above.

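### Aim 1 has no rule requiring both SD and SD/VT to differ from controls before an abnormality is called shared, and none for regions that come out as both shared and distinct

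*Combined protocol and SAP*

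**What the plan says.** The Aim 1 working hypothesis in Specific Aims is that "distinct brain abnormalities will be present in SD and SD/VT patients, who also share common abnormalities within the sensorimotor brain networks" that control voice. The analysis therefore has to sort regions into two classes.

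Section 1.3.1 (Study #1, group analysis) gives the only operational definition. The ANOVA, at a corrected 0.025, is run "to identify (1) shared abnormalities in all patients vs. controls, and (2) distinct abnormalities between SD vs. SD/VT patients". The same paragraph then restates the comparisons as "SD and SD/VT patients vs. controls and SD patients vs. SD/VT patients", which could mean one pooled contrast or two separate ones. The effective-connectivity paragraph of 1.3.1 uses similar shorthand.

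Aim 1 does not require each patient group to differ from controls, and does not say how to label a region that appears on both maps. A conjunction analysis is planned in section 2.3.1, but only for pre- and post-treatment scans in Aim 2. Sections 1.3.2 (VBM) and 1.3.3 (TBSS) compare groups without defining what makes a finding common.

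**The concern.** A pooled patient mean differs from the control mean whenever the two groups' deviations do not cancel, so one abnormal group is enough. The contrast tests whether patients are abnormal on average. The hypothesis is about abnormality in both disorders.

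The second planned contrast does not resolve this. A region significant on both fits two different situations: only SD/VT is abnormal, or both disorders are abnormal and SD/VT more so. Telling these apart is the purpose of Aim 1, and section 1.4 builds its expected diagnostic markers on the answer. The second situation is plausible: the pilot fMRI data in 1.2.2 show increases common to both groups and a greater extent of change in SD/VT.

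**Working it through.** **Inputs** (section 1.3.1, Study population and Sample size): "SD vs. controls: 0.63 ± 0.16 vs. 0.39 ± 0.23" percent signal change; two-sided test at 0.025; 20 recruited per group. A 0.005 voxel threshold with a cluster-size rule is stated in 1.3.1 for the individual maps and the group connectivity maps. For the group ANOVA the plan states only a corrected 0.025, so both levels are shown.

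**Step 1: the plan's own figure.** Difference = 0.63 − 0.39 = 0.24. Common SD = √((0.16² + 0.23²)/2) = 0.198. Standardised effect = 0.24/0.198 = 1.21. The noncentral t with 15 per group at two-sided 0.025 gives 82.3% power, and 15 is the smallest such n. This reproduces "a sample size of 15 subjects per group would have 80% power to detect group differences at a 0.025 significance level".

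**Step 2: what each contrast estimates.** Let a and b be the deviations of SD and SD/VT from controls. The pooled contrast estimates (a + b)/2 and the distinct contrast estimates b − a. With a = 0 and b = 0.24 they are 0.12 and 0.24, both non-zero. With a and b both positive and b larger, both are again non-zero. The pair of significance labels is the same in the two cases.

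**Step 3: how often the pooled contrast is significant when one disorder alone is abnormal.** There are 40 patients against 20 controls. SE = 0.198 × √(1/40 + 1/20) = 0.0543. Noncentrality = 0.12/0.0543 = 2.21 on 57 df. The critical values are 2.302 at 0.025 and 2.920 at 0.005.

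| One disorder abnormal, single test, 20 per group | 0.025 | 0.005 |
|---|---|---|
| Pooled contrast significant (57 df) | 47% | 25% |
| ANOVA contrast, simulated with unequal SDs | 42–52% | 22–31% |
| Pooled two-sample or Welch t-test, simulated | 33–41% | 15–21% |
| Both groups differ from controls, same direction | 1.2% | 0.2–0.3% |

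In the unequal-SD rows the unaffected patient group was given an SD of 0.16 or 0.23. With 15 per group the first figure at 0.025 falls from 47% to 35%.

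**Step 4: overlap with the distinct map.** In simulation with the common SD, 44 of the 47 percentage points at 0.025, and 21 of the 25 at 0.005, are also significant for SD versus SD/VT. With unequal SDs, a region is significant on the pooled contrast alone in 0.4–4% of runs at 0.025 and 1–6% at 0.005.

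**Step 5: the price of a conjunction.** If both disorders truly carry the 0.24 effect, single-test power is 98% (pooled) against 89% (conjunction) at 0.025, and 93% against 71% at 0.005.

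**The case against.** The strongest reply is that pooling is only one reading. The restatement in 1.3.1 can be read as separate comparisons, the pilot results in 1.2.2 are described group by group, and the sample size rests on a two-group SD-versus-control test. This stands as a genuine ambiguity. It does not close the gap, because even on that reading nothing says that both comparisons must be significant.

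A reader might infer that a one-disorder region would be declared shared about half the time. The documents do not support that. The 47% is for one test at an uncorrected 0.025, whereas the plan's 0.025 is a corrected level. At the 0.005 voxel threshold the rate is 15–31% across test versions, and a cluster-size rule would change it further. Nearly all of these regions would also be flagged as distinct, so a clean false label of shared is uncommon.

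A reader might also object that the pooled contrast misses regions changing in opposite directions. This adds little: such a region is not a shared abnormality in the plan's sense, SD versus SD/VT is well placed to detect it, and the pilot reports the common changes in the same direction in both groups.

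Nor do 1.3.2 and 1.3.3 state a pooled rule for VBM or TBSS. There the gap is a missing definition of common.

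**Conclusion.** The concern holds in this form: the only stated test of shared can be met by one disorder alone, and no conjunction or overlap rule corrects for it. If the plan's SD-versus-control effect sits wholly in one disorder, the pooled contrast is significant in roughly 15–50% of single tests, depending on threshold and test version, against about 1% or less for a conjunction. The usual consequence is a region labelled both shared and distinct, with no way in the plan to decide between one disorder only and both in differing degree.

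The size rests on assumptions. The effect from one region in an earlier SD study is applied to either disorder, the other disorder has exactly none, all 20 per group are analysed, and one test is considered at a time. Spatial dependence and cluster inference were not modelled. The structural point depends on none of these.

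**What to change.** In the group-analysis paragraph of 1.3.1, before analysis:

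- Define shared as SD versus controls and SD/VT versus controls each significant at the corrected threshold in the same direction (a minimum-statistic conjunction within the same ANOVA).
- Keep SD versus SD/VT as the test for distinct.
- State the overlap labels. Conjunction met and SD versus SD/VT significant: shared but differing in degree. SD versus SD/VT significant and only one group different from controls: disorder-specific.
- Report the pooled contrast only as an average patient effect.
- Apply the same definitions in 1.3.2 and 1.3.3 wherever VBM or TBSS findings are called common or distinct.

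No new data, scans or participants are needed. The cost is the loss of power in Step 5, which is modest at 0.025 and material at 0.005. The plan should acknowledge it, so that a region failing the conjunction is not read as proof that one disorder is spared.

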1.3.1 Study #1: Mapping disorder-specific brain activation in patients with SD vs. SD/VT using fMRI during symptomatic voice and speech production. We will use a sparse-sampling event-related BOLD fMRI design on a 3.0 Tesla Philips MRI scanner. We already successfully used this design for the investigations of voice and other laryngeal behaviors (Loucks et al., 2007; [name] et al., 2007; [name] et al., 2009; [name] and Ludlow, 2010). Brain activity will be studied during production of 10 symptomatic speech sentences (e.g., "We eat eels every day", "Sam has a rabbit in his hand") and syllables (repetitive vowel /i/ and continuous vowel /i/). In the scanner, subjects will listen to an auditory example of the task presented in a pseudorandomized order and reproduce it within the 5-s interval of the 'silent' period of scanning, only after which a 2-s image acquisition will follow, while the subjects remain silent and motionless. A resting condition without auditory presentation will serve as a baseline. Four scanning sessions will be acquired with a total of 36 experimental trials and 24 baseline conditions. Structural MRI will be acquired for an anatomical reference.

Data analysis will follow the similar processing pipeline as previously employed by us using AFNI software ([name] et al., 2007; [name] et al., 2009; [name] and Ludlow, 2010). Following initial data processing, the task-related responses will be analyzed using multiple linear regression with a single regressor for each task convolved with a canonical hemodynamic response function. Baseline drifts will be modeled using quadratic polynomials in time for each separate imaging run, and motion parameter estimates will be used as additional regressors of no interest in the multiple regression analysis. To account for disorder-specific vocal motor differences between SD and SD/VT groups, such as adductor and abductor voice breaks and shakiness, respectively, we will include the number of voice breaks and severity of voice tremor as variables in a within-group statistical analysis. Quantitative measures of SD and VT symptoms will be derived from the *Study 1.3.3* within this Aim. The correction of individual statistical parametric maps for multiple comparisons will be performed using Monte-Carlo simulations (Forman et al., 1995), which will identify a minimum cluster size at a voxelwise threshold of 0.005 at overall significance level of a corrected $p \leq 0.025$.

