Once such regions are identified, the group peaks of activation in these regions will be used as 4-mm seed regions for functional connectivity analysis ([name], 2003) using AFNI software to determine the *trait characteristics* of voice-controlling networks in SD and SD/VT. For this, we will use psychophysiological interactions (PPI) analysis, which refers to significant changes in the contribution of one brain region's activity to that in another region due to changes in the experimental or psychological context (Friston et al., 1997). Time series during task production and silent fixation will be extracted from each seed region in each subject and multiplied by the task vector with the follow-up regression with the time series from the entire brain. The results of regression analysis will indicate the changes in interaction of the seed region with the entire brain relative to the examined condition (e.g., speech vs. silent fixation). A significant change in interaction will mean that the functional connectivity between the seed region and a given region in the brain is significantly different when the subjects perform one task compared with another. The subject-specific functional connectivity maps will be submitted to group analyses to identify differences within and between the groups at a corrected $p \leq 0.025$ to account for multiple comparisons. To further correct for multiple comparisons across the voxels in the whole brain at a group $p \leq 0.025$, we will esti-

mate the voxelwise probability of a false positive detection using Monte Carlo simulation with the individual voxel probability threshold of $p \leq 0.005$ and data-dependent minimum cluster size threshold.

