Study population and Sample size. To estimate the number of subjects in this study, we reviewed our recent DTI studies, which used a similar experimental design to examine white matter abnormalities in SD patients and controls ([name] et al., 2008; [name] et al., 2009). Significantly decreased FA was found in the right genu of the internal capsule in SD (patients vs. controls: 0.55 ± 0.05 vs. 0.61 ± 0.07). Using these values, a power of 80% at a 0.025 significance level will be obtained with 18 subjects per group for the proposed study based. Again, to increase the statistical significance and allow for between-study comparisons, we propose to recruit the same 20 subjects per SD, SD/VT and control group for the DTI study. The statistical power for tractography is the same.

1.3.4 Study #4: Relationship between brain abnormalities and clinico-behavioral characteristics in SD and SD/VT.

The role of neuroimaging studies in elucidation of pathophysiological mechanisms of SD would be considerably enhanced if coupled with strategies that yield information about their relevance to symptom elicitation. Additionally, identification of disorder-specific brain abnormalities that are correlated with disorder symptoms can prove useful for assessment of efficacy of existing and newly developed therapeutic interventions. Our approach here will be to examine the relationships of functional brain activity and structural brain organization with clinico-behavioral correlates (i.e., disorder severity scores). For all 20 subjects per group (both patients and controls), the behavioral measures will be obtained during initial intake screening, history and physical examination, and three-tiered diagnostic questionnaire (see *Appendices 1 and 2*). Patients' voice and speech will be digitally recorded during scanning for offline acoustic analysis to assess the SD and VT severity.

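### The Aim 1 power figures describe one uncorrected patient-versus-control test in one region; the planned group tests are corrected across the brain, and equal power for network and tractography analyses is asserted without a calculation

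*Combined protocol and SAP*

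**What the plan says.** Section 1.3.1 (Study population and Sample size) takes its effect size from an earlier study by the same team: "Significantly increased activation intensity was found in the primary somatosensory cortex during production of symptomatic syllables in SD patients compared to controls", with percent signal change of "SD vs. controls: 0.63 ± 0.16 vs. 0.39 ± 0.23". The section applies a t-test, described as two-tailed, to these values and concludes: "a sample size of 15 subjects per group would have 80% power to detect group differences at a 0.025 significance level". Next comes "The power for network analyses is the same". The plan recruits 20 per group, partly to cover dropout, and gives no dropout rate.

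Sections 1.3.2 and 1.3.3 follow the same pattern:

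- **Gray matter volume (1.3.2):** laryngeal sensorimotor cortex, 0.22 ± 0.04 in controls and 0.26 ± 0.04 in SD; 17 per group for 80% power at 0.025.
- **Fractional anisotropy (1.3.3):** right genu of the internal capsule, 0.55 ± 0.05 in patients and 0.61 ± 0.07 in controls; 18 per group for 80% power at 0.025. The section closes with "The statistical power for tractography is the same".

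Neither section says whether its test is one- or two-sided.

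The analysis text of the same sections sets these criteria:

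- **Single-subject fMRI maps:** Monte Carlo simulation, "which will identify a minimum cluster size at a voxelwise threshold of 0.005 at overall significance level of a corrected" 0.025.
- **Group activation ANOVA:** 0.025, described as voxelwise corrected. No 0.005 threshold is given here.
- **Group PPI maps:** each seed against the whole brain, using "Monte Carlo simulation with the individual voxel probability threshold of" 0.005 plus a minimum cluster size, at group 0.025.
- **DCM:** corrected 0.025, on parameters between regions of interest.
- **VBM:** cluster-level 0.025.
- **TBSS:** adjusted 0.025 over the white matter skeleton.
- **Tractography:** maps between regions of interest, at a corrected 0.025.

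**The concern.** An uncorrected 0.025 in one region and a corrected 0.025 over a brain-wide search are different criteria, and the second is harder to meet for the same effect. The sample-size paragraphs use the first, the analysis paragraphs use the second, and the shared figure of 0.025 hides the difference. None of the three regions behind the sample sizes is named in the analysis text as a test in its own right.

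The equal-power sentences raise a separate problem. PPI interaction terms, DCM coupling parameters and tractography connectivity are different quantities from percent signal change and regional FA. Means and standard deviations of the latter say nothing about the variance or effect size of the former.

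All three effect sizes also compare patients with controls. The question that distinguishes Aim 1 is SD versus SD/VT, and no effect size is offered for it.

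What is at stake is how a null result is read. A blank group map, an unchanged connection or no SD versus SD/VT difference would be taken as coming from a test with 80% power, which the plan has not shown.

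**Working it through.** **Method.** Two-sample t-test, n per group, pooled SD = √((s₁² + s₂²)/2), d = difference / pooled SD. Power comes from the noncentral t distribution with 2n − 2 degrees of freedom and noncentrality d·√(n/2). All inputs are the means and SDs in the three sample-size paragraphs.

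**Step 1: reproduce the fMRI figure.**

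- Difference = 0.63 − 0.39 = 0.24.
- Pooled SD = √((0.16² + 0.23²)/2) = √(0.0785/2) = 0.198.
- d = 0.24/0.198 = 1.21.
- n = 15, two-sided 0.025: noncentrality 1.211 × √7.5 = 3.32, critical t (28 df) 2.37, power 82.3%.
- n = 14 gives 79.0%, so 15 is the smallest size reaching 80%.

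The stated 15 is correct for one uncorrected comparison. With 20 completers per group the same test has 92.8% power.

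**Step 2: the other two modalities.**

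- Gray matter: d = 0.04/0.04 = 1.00.
- FA: pooled SD = √((0.05² + 0.07²)/2) = √(0.0074/2) = 0.0608; d = 0.06/0.0608 = 0.99.

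| Test | Stated n | Power, two-sided 0.025 | Power, one-sided 0.025 | n for 80%, two-sided 0.025 | Power at n = 20, two-sided 0.025 |
|---|---|---|---|---|---|
| S1 activation | 15 | 82.3% | 89.3% | 15 | 92.8% |
| Laryngeal sensorimotor GMV | 17 | 71.2% | 80.7% | 21 | 79.3% |
| Right genu FA | 18 | 72.8% | 82.0% | 21 | 78.1% |

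The 17 and 18 are the smallest sizes for 80% only at one-sided 0.025, which is the same as two-sided 0.05. The 15 is the smallest size only at two-sided 0.025. The three figures therefore rest on two different conventions.

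**Step 3: what a stricter threshold does to the fMRI effect.** The documents give no smoothness, search volume or minimum cluster size, so power after whole-brain correction cannot be computed. As a guide, take d = 1.21 at a single voxel tested two-sided at 0.005:

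- n = 15: noncentrality 3.32, critical t 3.05, power 60.9%.
- n = 20: noncentrality 1.211 × √10 = 3.83, critical t (38 df) 2.98, power 79.5%.
- 80% power needs 21 per group.

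These figures leave out the cluster-size requirement and dropout. In Aim 1 the 0.005 applies to single-subject maps and group PPI maps only, so this shows how sensitive power is to the threshold. It is not the power of the group ANOVA.

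**Step 4: SD versus SD/VT.** No effect size is given. If it were half the patient-versus-control fMRI effect (an assumption, d = 0.61), power with 20 per group would be 35% at two-sided 0.025 and 16% at 0.005.

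**Step 5: network and tractography analyses.** There is nothing to compute, because no mean, SD or effect size is given for any PPI, DCM or tractography measure.

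**The case against.** The plan is open about its basis: each paragraph names the region and the values used, so a careful reader can see that the figure is specific to that region. The fMRI arithmetic is right. The plan enrols 20 per group, not 15, and at 20 even a 0.005 single-voxel test keeps 79.5% power for the S1 effect if nobody drops out. The pilot work in 1.2.2 reports shared and distinct differences, including SD versus SD/VT, at a corrected 0.01 with 7 to 10 subjects per group.

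Most of this stands as fact and limits the point. Naming the region does not turn the figure into the power of a brain-wide test, and it does not support the two equal-power sentences. The pilot results are evidence of feasibility and supply no effect size from which power could be calculated.

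A reader might infer that every planned group test uses a 0.005 voxel threshold and falls well short of 80%. The documents do not support that. For Aim 1 group tests, 0.005 is stated only for PPI; its other appearance concerns single-subject maps. The group ANOVA, VBM and TBSS state a corrected 0.025 with no 0.005. DCM and tractography work between regions of interest, so their defect is the missing calculation, not a whole-brain search.

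**Conclusion.** The concern holds in this form: the 80% power in 1.3.1 to 1.3.3 belongs to a single-region, uncorrected comparison of SD patients with controls. It is not shown for the corrected group maps, for the PPI, DCM and tractography analyses, or for SD versus SD/VT. The accurate description is that power is not demonstrated; the documents do not allow the stronger statement that it is below 80% by a known amount.

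For the single-region tests, power with 20 completers per group at two-sided 0.025 is 93%, 79% and 78%. The guide figures of 61% and 79.5% at a single 0.005 voxel assume the published S1 effect carries over unchanged and ignore the cluster-size rule and dropout. The 71% and 73% for the gray matter and FA sample sizes assume that the two-sided convention stated for fMRI was meant throughout, since those two paragraphs do not state sidedness.

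**What to change.** 1. In the sample-size paragraphs of 1.3.1, 1.3.2 and 1.3.3, say that the power figure applies only to a single-region, uncorrected patient-versus-control comparison at 0.025. At two-sided 0.025 with 20 completers per group it is 93% for S1 activation, 79% for laryngeal sensorimotor GMV and 78% for right genu FA.
2. Bring 1.3.2 and 1.3.3 into line. Either restate 17 and 18 per group as giving 71% and 73% at two-sided 0.025 (80% needs 21), or state and justify a one-sided test.
3. Delete "The power for network analyses is the same" and "The statistical power for tractography is the same".
4. Add that the whole-brain, PPI, DCM, tractography and SD versus SD/VT comparisons have no demonstrated power, so a null result in any of them is not evidence of no difference.

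Region-of-interest tests in the three named regions may be added as supportive analyses of data already being collected. They need not become primary: that would be a redesign, would raise its own multiplicity question and would sideline SD versus SD/VT.

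The cost is a few sentences, with no new subjects or scans. The power claim becomes narrower, and for gray matter and FA it falls slightly below 80% even with all 20 per group completing.
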